1.3 Exploratory Objectives

- 1.3.1 To measure the baseline levels of immune markers including CD8+ T effector cells and CD4+FoxP3+ T regulatory cells, PD-L1 expression and tumor infiltrating lymphocytes (TILs), major histocompatibility complex (MHC) class I and II expression, and natural killer (NK) cell receptors and ligands expression and correlate these variables with treatment response and toxicity.
- 1.3.2 To characterize changes in the immune markers described above after treatment

1.3.3 To identify gene expression changes in malignant tissue after therapy, and complete gene set analysis to elucidate affected pathways

1.3.4 To measure changes in circulating immune suppressor cells (myeloid derived suppressor cells (MDSC), Treg) in peripheral blood by flow cytometry and test for association with response to therapy.

1.3.5 To assess the baseline characteristics of the subjects enrolled and to correlate these molecular and clinicopathologic criteria with treatment response and toxicity.

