1.6 Exploratory Endpoints

- **1.6.1** Changes in immune-related biomarkers (e.g., expression of checkpoint receptors (PD1/PD-L1), the number of MDSCs, inflammatory T cell signature, in tumor biopsies and peripheral blood pre- and post-therapy and their correlation with response to therapy.
- **1.6.2** Gene expression changes in circulating DNA and malignant tissue after therapy, and complete gene set analysis to elucidate affected pathways
- **1.6.3** Changes in circulating immune suppressor cells (MDSC, Treg) in peripheral blood by flow cytometry and test for association with response to therapy

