4. TREATMENT PLAN

4.1 Agents Administration

Treatment will be administered on an outpatient basis. Reported adverse events and potential risks are described in **Section 6**. Appropriate dose modifications are described in **Section 5**.

No investigational or commercial agents or therapies other than those described below may be administered with the intent to treat the patient's malignancy.

The cycle length is 28 days. Treatment will consist of the combination of entinostat and nivolumab. A lead-in of entinostat 2 weeks prior to combination therapy at the dose of 5 mg/weekly, will be incorporated to help determine the effect of entinostat on immune-related parameters in tumor biopsies.

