4.2 Overall Study Design

The proposed study single institution, open-label, two-stage, phase 2 study evaluating the clinical activity and safety of entinostat plus nivolumab. We will enroll two cohorts of patients: unresectable or metastatic cholangiocarcinoma (Cohort 1) and unresectable or metastatic pancreatic adenocarcinoma (Cohort 2). The primary objective of the trial is to determine whether the combination of entinostat plus nivolumab yields a clinically compelling antitumor activity measured as objective response rate (ORR, assessed by RECIST 1.1).

Secondary endpoints include safety, progression-free survival (PFS), overall survival (OS), and immunologic correlates.

The study is planned with 27 evaluable subjects per histology based on a two-stage design that allows early termination for lack of efficacy.

Patients will receive a biopsy at baseline and on approximately day 14 of entinostat therapy and approximately after 6 weeks from Cycle 1 Day 1. An optional biopsy will be performed at the time of disease progression. After a fourteen-day lead in with entinostat monotherapy, patients will begin to concurrently receive entinostat 5 mg oral once a week plus nivolumab 240 mg every two weeks for approximately four months. After 4 months, nivolumab will be given at a dose of 480 mg fixed dose every 4 weeks (maintenance phase). Therapy may continue with entinostat 5 mg weekly plus nivolumab 480 mg every 4 weeks, until intolerance or progression. Nivolumab will be administered intravenously over a period of 30 minutes.

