9. BIOMARKER, CORRELATIVE, AND SPECIAL STUDIES

9.1 Overview

The major hypothesis of our correlative studies are that:

- 1) Treatment with entinostat will result in changes in TME enhancing T cell effectors and/or reducing suppressive ability of CD4+FoxP3+ T regulatory cells and MDCSs in the tumors.
- 2) Immunologic changes in biopsy specimens will correlate with subsequent clinical response to anti-PD-1/PD-L1 therapy.

Explorative correlative studies will be performed on biopsy specimens (pre - and post- entinostat treatment and approximately after 6 weeks from Cycle 1 day 1) and blood samples.

Mandatory research bloods and tumor biopsies will be obtained at baseline (day -14), after two weeks of entinostat lead in period (on approximately day 14 from the first entinostat administration), and approximately after 6 weeks from Cycle 1 day 1 visit. (see Study Calendar, **Section 10**). Biopsies at progression are optional.

These three mandatory biopsies will provide valuable information regarding the mechanism of action of entinostat and the impact on the TME when PD1 inhibition is added in, as well as primary resistance mechanisms to the strategy.

NOTE: All samples will be collected as outlined below, initially processed, and stored/bank until future analysis.

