12.3.4 Analysis of Exploratory Endpoints

Exploratory correlative studies will be performed to investigate:

- To measure the baseline levels of immune markers including CD8+ T effector cells and CD4+FoxP3+ T regulatory cells, PD-L1 expression and tumor infiltrating lymphocytes (TILs), major histocompatibility complex (MHC) class I and II expression, and natural killer (NK) cell receptors and ligands expression and correlate these variables with treatment response and toxicity.
- To characterize changes in the immune markers described above after treatment
- To identify gene expression changes in malignant tissue after therapy, and complete gene set analysis to elucidate affected pathways
- To measure changes in circulating immune suppressor cells (MDSC, Treg) in peripheral blood by flow cytometry and test for association with response to therapy.

The overarching aim of these exploratory studies is to establish baseline levels and measure changes in immunological pathways after treatment. Little is known about baseline levels for these variables in Cholangiocarcinoma and Pancreatic Adenocarcinoma, let alone changes after treatment, and if the primary and secondary aims are successful, these investigations will establish a biological foundation on which to build in follow-up studies.

Immunological variables will be examined in plots and summary statistics, to characterize distributions, identify outliers and other potential problems in the data. Joint exploratory analysis will identify associations and potential interactions. Variables may be transformed on the basis of these investigations, to reduce skewness, minimize the influence of outliers and/or to regularize relationships between predictors and response for better model fit. Exploratory analysis of the molecular markers, including visualizations and statistical summaries such as hierarchical cluster analysis, heat maps, multidimensional scaling, and principle component analysis will offer important views of the structural characteristics of the expression data.

Response will be described categorically, and associations between response and immunological variables will be characterized, in each cohort, using multivariate logistic regression models, with adjustment for clinical and pathological co-variates that may be associated with response. Estimated effects will be reported with standard errors and confidence intervals.

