We will fit empirical Bayes linear models [129] to identify genes for which expression is associated with response to treatment, controlling type I error at an FDR of <10%. Gene set enrichment analysis [130, 131] will be applied to the results to identify immune pathways that are significantly altered after treatment.

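### The only gene-level model tests association with clinical response, yet enrichment on its results is to be read as pathways altered by treatment; no before/after gene-level contrast is stated

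*Combined protocol and SAP*

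**What the plan says.** **The question asked.** Objective 1.3.3 is "To identify gene expression changes in malignant tissue after therapy, and complete gene set analysis to elucidate affected pathways". Endpoint 1.6.2 is "Gene expression changes in circulating DNA and malignant tissue after therapy, and complete gene set analysis to elucidate affected pathways". Section 12.3.4 repeats the tissue objective and adds: "The overarching aim of these exploratory studies is to establish baseline levels and measure changes in immunological pathways after treatment". Section 4.1 gives the purpose of the two-week entinostat lead-in: it "will be incorporated to help determine the effect of entinostat on immune-related parameters in tumor biopsies". Section 9.1 makes three biopsies mandatory (baseline, about day 14 of entinostat, and about week 6 from Cycle 1 Day 1), expecting "valuable information regarding the mechanism of action of entinostat and the impact on the TME when PD1 inhibition is added in".

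**The analysis stated.** Section 12.3.4 gives one gene-level inferential model: "We will fit empirical Bayes linear models [129] to identify genes for which expression is associated with response to treatment", with an FDR limit below 10%. Enrichment is then specified: "Gene set enrichment analysis [130, 131] will be applied to the results to identify immune pathways that are significantly altered after treatment". The only other methods named for expression data are clustering, heat maps, multidimensional scaling and principal components. Section 9.3 describes assays and sequencing, not statistical contrasts. No section states which biopsy's expression values, or whether a change score, enter the response model.

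**The concern.** The question is about change over time within patients. The model compares patients who respond with patients who do not. Enrichment takes the ranking from the second and reports it as an answer to the first. Two things can go wrong.

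- A treatment effect present in every patient, such as a uniform pharmacodynamic effect of entinostat, would be missed.
- If levels rather than changes enter the model, a pathway that separates responders from non-responders at both times, but does not move, could be reported as altered by treatment.

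What is at stake is the interpretation of the serial tumour biopsies and the biological groundwork that section 12.3.4 wants for follow-up studies. No decision about efficacy or stopping depends on it.

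**Working it through.** **1. Why the two questions differ.** For one gene, let baseline expression be B and post-treatment expression P = B + δ + noise, where δ is a change common to all patients. Let θ be a responder/non-responder difference present at both times. The contrasts then estimate:

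| Contrast | Estimates |
|---|---|
| Response model on baseline values | θ (δ is not in the data) |
| Response model on post-treatment values | θ + δ − δ = θ |
| Response model on change scores | δ − δ = 0 |
| Paired before/after | δ |

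No version of the response model contains δ. The two versions on levels contain θ, which is not a treatment effect. This needs no numerical assumption.

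**2. Illustration of size.** The documents give no effect sizes, so every input here is assumed:

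- 1000 independent genes: 100 shifted in every patient, 100 with a responder difference at both times and no change, 800 null.
- Unit variance and within-patient correlation 0.5, so the paired difference has SD √(1 + 1 − 2×0.5) = 1.
- 27 pairs, 5 responders, ordinary t tests, Benjamini-Hochberg at 10%.

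With a shift of 1 SD and a responder difference of 2 SD, the share of genes flagged is:

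| Test | Shifted genes | Response-linked, unchanged genes |
|---|---|---|
| Paired | 98.9% | 1.0% |
| Response model, baseline | 0.92% | 87.8% |
| Response model, post-treatment | 0.97% | 87.8% |
| Response model, change score | 0.02% | 0.01% |

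The figures near 1% are not weak detection. They stay at about 0.9–1.1% on levels when the shift is cut to 0.75 or 0.5 SD, and they fall to about 0% when no gene is response-linked. They are the false discoveries that the procedure tolerates once the response-linked genes are found. The last column depends strongly on the assumed responder difference: on levels it is about 51% at 1.5 SD and 6% at 1 SD.

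**3. A cohort that stops early.** Section 12.2 stops at 0 responders in 13.

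- At 5% ORR: 0.95^13 = 0.513, which reproduces the plan's 51%.
- At 20% ORR: 0.80^13 = 0.055.

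If response in the gene model means CR/PR, there is then no group to compare and the model cannot be fitted in that cohort. A paired contrast can. With a 1 SD shift it finds 64%, 33% or 9% of shifted genes with 13, 10 or 8 pairs by ordinary t tests. With moderated tests, the type the plan names, it finds 83.8%, 68.5% or 51.7%; those figures are optimistic because all simulated variances are equal.

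**The case against.** **The response model has its own purpose.** Endpoint 1.6.1 asks for correlation of biomarker changes with response. The second hypothesis in section 9.1 is that immunologic changes in biopsies correlate with later clinical response. A reader might infer that the model is misplaced, or that the biopsies exist only to show treatment change. The documents do not support that: the model should stay, and only the label on its enrichment is wrong. Section 4.1 also speaks of immune-related parameters, which immunohistochemistry serves as well.

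**Change scores may be intended.** The section 9.1 hypothesis makes this plausible. If so, the mislabelling of unchanged pathways does not arise. The missed common change remains, because a model of change scores by response asks whether change differs by response, not whether expression changed.

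**Response need not mean CR/PR.** Section 12.3.4 says only that response is categorical. If stable and progressive disease were separate categories, a cohort stopped at 0/13 might still be modelled. A reader might infer that such a cohort certainly has no gene-level analysis; that is conditional.

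**Compressed drafting.** Empirical Bayes linear models can take a time term, and the change aim is restated in the same section, so the authors may have meant to fit one. That may be so, but no time term, blocking factor or biopsy time point is named, and enrichment is tied explicitly to the response results. Molecular response is an unlikely reading, since the preceding paragraph relates categorical response to immunological variables by logistic regression.

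**Low stakes.** This stands, and it sets the severity.

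**Conclusion.** The point holds as a mismatch between objective and analysis: as written, the plan contains no gene-level test of change for objective 1.3.3 or endpoint 1.6.2, and it attaches a conclusion about change to a test of something else. That rests on the text and on the algebra in step 1 alone.

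The size (about 99% against about 1% or less) is an illustration under assumed inputs, not a forecast. Mislabelling of unchanged pathways depends on levels entering the model. The early-stopping consequence depends on response meaning CR/PR.

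A reader might infer that the trial's conclusions are at risk. They are not: the ORR test, the stopping rule and the safety analyses do not use these results. Severity is minor.

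**What to change.** 1. Keep the response model and its enrichment for the response-correlation aims. Label the output as associated with response, say how response is categorised, and state which time point or change score enters.
2. Add, in each cohort, an empirical Bayes model with patient as block and biopsy time as the effect, at FDR below 10%. Week 6 v baseline is the direct answer to 1.3.3. Further contrasts are day 14 v baseline (the entinostat lead-in) and week 6 v day 14. The last is not a pure nivolumab effect, because after the lead-in "patients will begin to concurrently receive entinostat 5 mg oral once a week plus nivolumab 240 mg every two weeks".
3. Run the enrichment that is to be read as altered after treatment on these contrasts. Report the number of pairs in each, since section 9.2.1 allows later biopsies to be waived.
4. Apply the same before/after contrast to the circulating DNA part of 1.6.2, or state that it is not analysed.

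The cost is SAP wording and routine code on samples already planned. The limits to disclose are a little more analysis, incomplete pairs that may not be missing at random, weak contrasts if pairs are few, and no control group, so a before/after change also contains elapsed time and any change of biopsy site.

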14. APPENDICES

Appendix A: Eastern Cooperative Oncology Group Performance Status Scale, with Equivalent Karnofsky Performance Status Scores

	ECOG ¹		Karnofsky ²
Score	Criterion	%	Criterion
0	Normal activity	100	Normal; no complaints; no evidence of disease
		90	Able to carry on normal activity; mine signs or symptoms of disease
1	Symptoms but ambulatory	80	Normal activity with effort; some signs or symptoms of disease
		70	Cares for self; unable to carry on norm activity or do active work
2	In bed <50% of time	60	Requires occasional assistance but is abl to care for most of his/her needs
		50	Requires considerable assistance ar frequent medical care
3	In bed >50% of time	40	Disabled, requires special care and assistance
		30	Severely disabled; hospitalization indicated though death is not imminent
4	100% bedridden	20	Very sick; hospitalization is necessary
		10	Moribund; fatal processes progressing rapidly
5	Dead	0	Dead

¹Oken MM, Creech RH, Tormey DC, Horton J, Davis TE, McFadden ET, Carbone PP. Toxicity and response criteria of the Eastern Cooperative Oncology Group. Am J Clin Oncol. 1982;5:649-655.

Appendix C: Entinostat Drug Diary

Subject ID: , Subject Initials: , Cycle #:

Directions:

- Use this diary to record each dose of entinostat that you take.
- You should take your scheduled dose of each pill. If you miss a dose and it is within 24 hours of when it should have been taken, you should take the dose. If it has been more than 24 hours of when you should have taken the dose, call the study staff. Do not "doubleup" to try and make-up missed doses.
- Entinostat should be taken on an empty stomach, at least 1 hour before or 2 hours after a meal/snack.
- Please bring the empty bottle or any leftover tablets and your pill calendar to your next clinic visit.
- If you develop any side effects, please record them and anything you would like to tell the doctor in the space provided.

Assigned entinostat dose:	mg
Start date of calendar:	

Signature of Participant

Number of pills to take at each dose:

Date	Entinostat		Comments
(Month / Day / Year)	# pills	Time	(such as side effects, symptoms, other medication
		A. A. A. CON. 5	
		Date Enti (Month / Day / Year) # pills	

Additional information (if needed):

	Date	1		Comments		
Week	(Month / Day / Year)			(such as side effects, symptoms, other medications)		
1						
2						
3						
4						
Additional information (if needed):						

Completed by:

Date:

Reviewed by: _____ Date: _____

Appendix D: Management Algorithms for Nivolumab -Related Adverse Events

Adverse Event Management Algorithms:

GI Renal Pulmonary Hepatic Endocrinopathy Skin Neurological J1798/Version 5.0/May 21, 2020

Appendix E: Concomitant Medications to be Avoided

Examples of sensitive *in vivo* CYP substrates and CYP substrates with narrow therapeutic range are summarized in *Table 14.1*

CYP Enzymes	Substrates with narrow therapeutic range ¹					
CYP1A2	Theophylline, tizanidine					
CYP2C8	Paclitaxel					
CYP3A ²	Alfentanil, astemizole ³ , cisapride ⁴ , cyclosporine, ihydroergotamine, ergotamine, fentanyl, pimozide, quinidine, sirolimus, tacrolimus, terfenadine ⁴					

Table 14.1 Examples of substrates that may be affected by entinostat

¹ CYP substrates with narrow therapeutic range refers to drugs whose exposure-response relationship indicates that small increases in their exposure levels by the concomitant use of CYP inhibitors may lead to serious safety concerns (e.g., Torsades de Pointes).

² Because a number of CYP3A substrates (e.g., darunavir, maraviroc) are also substrates of Pgp, the observed increase in exposure could be due to inhibition of both CYP3A and P-gp.

³ Withdrawn from the United States market because of safety reasons.

Refer to *Table 14.2* for examples of transporter inhibitors and inducers.

Table 14.2 P-gp Inhibitors and Inducers

	Inhibitor	Inducer			
P-gp, MDR1	Amiodarone, azithromycin, captopril, carvedilol, clarithromycin, conivaptan, diltiazem, dronedarone, felodipine, lopinavir,quercetin, ranolazine,ticagrelor, ritonavir, cyclosporine, verapamil erythromycin, ketoconazole, itraconazole, quinidine	Avasimibe, carbamazepine, phenytoin, rifampin, St John's Wort, tipranavir/ritonavir			

J1798/Version 5.0/May 21, 2020

Protocol Title: A Phase 2 Clinical Trial of Entinostat in Combination with Nivolumab for Patients with Previously Treated Unresectable or Metastatic Cholangiocarcinoma and Pancreatic Adenocarcinoma **Protocol Number:** Signature of PI: **Principal Investigator:** Date: J1798 CA209-9L6 SNDX-275-0205 **Report Type:** Serious Criteria (check **Hospital Admission** Date Event Initial Discovered: all that apply): Date: Follow-up Death Final Follow-up Life-threatening Hospitalization or Death Addendum to: Elongation of Existing **Hospital Discharge Date:** Hospitalization Persistent or Significant Disability Congenital Anomaly Other Important Medical Event Cancer Overdose Section A: Subject Information Subject ID: Subject Initial: DOB: Subject Gender: Male Female Section B: Event Information or Date of First Dose: Event diagnosis Action taken with the symptoms: study drug: Entinostat Nivolumab None Interrupted Date of Last Dose Prior to Discontinued Event: Delayed Nivolumab Entinostat Number of Total Doses: Entinostat Nivolumab

Appendix F: Serious Adverse Event Reporting Form

Event Onset Date:	Event End Date:									
Relationship to:		Entinostat	Nivolumab		Underlying Disease					
Unrelated										
Related										
Section C: Brief Description of the Event:										
Section D: Relevan	t Medical His	story								
Section E: Concomitant Drug (Not related to SAE)										
Name of the Drug	Start Date	Stop Date		Do	se	Frequency				
		14								
Section F: Commen	nts									
Additional Documents: Please specify
